MBC addresses many of the limitations that have restricted the reach of many other youth mental health practices. First, many EBPs are designed to address single diagnoses or clusters similar disorders, whereas comorbidity rates are high in youth psychopathology.¹⁵ This single-problem focus may decrease real-world effectiveness, and make EBPs less appealing to clinicians, who are concerned that they are not relevant to their clients^{25,26}. A second, related problem is that clinicians face a significant training burden to become competent in the many single-problem EBPs that would be necessary to cover their caseloads.²⁸ Third, surveys of clinicians indicate they perceive many EBPs as too rigid for personalized treatment^{25,29}, whereas their attitudes toward MBC and other EBPs that cut across multiple diagnostic groups are positive^{22,23}. MBC is a transdiagnostic intervention that supports personalized treatment across an agency’s full caseload, increasing its utility and appeal. MBC can be leveraged to inform clinician utilization of a range of interventions, including being embedded as “clinical dashboards” to guide use of other EBPs²⁴.

A significant barrier to advancing the use of MBC is a lack of research that tests the mechanisms underlying effective MBC. MBC is founded upon the premise that high-quality and continuous feedback will improve clinician competency, enhancing client outcomes⁵³. In typical care, clinicians receive limited standardized information client outcomes^{51,52}, often make inaccurate appraisals of their own competence⁵⁴, and hence fail to make adjustments to their practice when needed. MBC alerts clinicians to clients who are not responding to treatment, prompting them to change therapeutic strategies⁵⁵⁻⁵⁷. Clinicians may also share feedback results with clients, which could increase client engagement^{58,59} and enhance therapeutic alliance^{60,61}. One study has shown a link between problems identified in feedback reports and content addressed in session²⁵, suggesting that MBC feedback can influence clinician behavior.

However, the underlying mechanisms of action of MBC remain largely theoretical. Research is needed that explicitly investigates MBC mechanisms in order to enhance MBC effectiveness and improve implementation support.

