Procedures for effectiveness trial. After Aim 1 is complete, program-wide implementation of MBC will begin. The initial training will consist of a series of workshop style trainings conducted during regular agency staff meetings and ongoing consultation will be provided to agency staff thereafter. The training approach is a data-driven one, where questionnaires are used throughout the training and consultation to tailor implementation to that specific context. These questionnaires will be considered part of the implementation activities and will be administered to all staff members participating in the trainings. Clinicians who consent to be in the research study will be giving permission for these implementation data to be linked to the research data they provide for their clients; responses from other HCA staff will be de-identified and used to characterize the implementation under Aim 3. Prior to extracting these data for research purposes, we will submit a variable list to the IRB for approval. When the initial training is complete, the trial will begin program-wide at the participating HCA clinics. As the clinics add clients ages 11-17 to the Mirah system, the system will automatically randomize them to either unidimensional or multidimensional MBC on a 1:1 ratio. All clients and their caregivers will complete MBC measures as part of routine services, and the researchers will receive limited identifier datasets containing MBC data and Mirah metadata for all participants, an identifiable

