Quantitative Analyses. Aims 1b and 2 will involve using multilevel modeling (MLM) approaches¹²⁵, to account for nesting of repeated measures within clients and clinicians. In all Aim 2 models, we will treat site as a fixed effect, due to the limited number of clinics (n=3). For **Aim 1b**, on-track (OT) and not-on-track (NOT) algorithms will developed using an extant dataset^{46,47} (N = 597). Analyses will progress in two stages, following established procedures previously applied to the Outcomes Questionnaire system¹¹⁸⁻¹²⁰, the most widely-tested MBC system¹⁹. The first stage of the analysis involves generating expected change trajectories for SFSS scores over time. MLM will be used to estimate these individual change trajectories with weekly scores nested within participants, who are in turn nested within therapists. Models will be tested using the Hierarchical Linear Modeling (HLM) software package¹²⁶ and restricted maximum likelihood (RML) estimation. Prior to hypothesis testing, we will examine SFSS distributions and apply transformations (e.g., square root, logarithmic) for the weeks in treatment variable as necessary¹¹⁸.

The second stage of the analysis involves: (1) developing a system to identify cases at risk of showing treatment deterioration (NOT), and (2) testing its predictive accuracy. Identification of NOT cases is based on the expected change trajectories (intercepts, slopes, and random effects) estimated in Stage 1. Following Cannon et al¹¹⁸, we will split the data into two random samples, a reference sample and a validation sample. As a first step, the base rate of treatment

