Aim 2b will investigate potential factors associated with condition, client, or clinician that could influence a future SMART. GLMM (MLM with a logistic linking function) will be used to investigate factors associated with treatment and attrition from the study. In addition, differences between the full RCT sample (N = 900) and the Research Subsample (N = 400) will be examined utilizing data from electronic health records (EHR) to determine whether enrollment in the Research Subsample, and completing all 12 weeks, is associated with any demographic or clinical factors. We will also examine enrollment and attrition rates for clients within clinicians to determine whether any clinician factors might be associated with client-level participation in the study, along with comparing enrollment rates across clinics. As above, these analyses will inform design of the R01 SMART, including power analyses that take into account rates of NOT/OT and projected attrition.

MLM will also be used to compare the effects of study condition on SFSS change trajectories, Ohio Scores, and MBC mechanisms (**Aim 2c**). We will examine differences in MBC outcomes by feedback condition, nesting within treating clinician and controlling for clinic. If sample sizes in the research subsample prove too small for this analytic approach, analyses of variance will be used to test a time by treatment interaction. As a first step in comparing conditions on MBC mechanisms, we will aggregate the scores across sessions (within therapist) by averaging them or summing count variables (e.g., matches between a client being identified as NOT and the therapist recognizing deterioration) to create composite variables for each mechanism domain in Figure 2.

Finally, we will extend the MLMs tested to accommodate potential mediators and moderation by NOT status, diagnosis, and treatment type (**Aim 2d**). Mediation will be tested using the products of coefficients method¹²⁹, using bootstrapping to adjust for nonnormal, asymmetric confidence intervals¹³⁰. Algorithms for testing mediation using these methods are available in the package RMediation¹³¹ available in the software platform R. Moderation by NOT status will be tested by entering NOT status, along with the feedback condition by NOT

status interaction and other model covariates. Similar models will examine moderation by diagnosis and treatment type.

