Sample size and power calculations. Given the preliminary nature of this pilot study, power calculations focused on power for the analyses of the group differences in outcomes (Hypothesis 2c.1). Power calculations were conducted using Optimal Design 3.1. We assumed 8% of the outcome variance at the clinician level¹³⁵ for an n of 22 clinicians (over the duration of the study) and 900 adolescents, $\beta = .80$, and $p = .05$. Using these estimates, Aim 2c, examining the impact of feedback condition on treatment response (assessed by the SFSS) will be optimally powered to detect a small effect of $d = .25$. The only previous estimate of differences between multidimensional and unidimensional MBC focused on the NOT subgroup only, finding an effect of ($d = .31$); the overall effect size for this study is expected to be smaller because the analyses will focus on the NOT and OT groups combined. Using a more conservative small effect size of $d = .20$ yields power of approximately .75. With respect to power assessing differences by feedback condition in the Research Subsample (n = at least 22 clinicians and 400 adolescents) will be optimally powered for a small-moderate effect of $d = .30$. Assuming an effect size of $d = .25$ yields power of .62.

DATA SECURITY, STORAGE, AND QUALITY CONTROL

Quantitative data will be collected electronically via either the University of Miami REDCAP system or directly through Mirah. Mirah is a HIPAA compliant system for collecting and scoring clinical measures. It uses Secure Sockets Layer (SSL) encryption to protect all data during transfers and stores is on a secure server. Data access will be restricted to study personnel, with permissions set to only those necessary to perform

tasks. Whenever possible, staff will download data directly from REDCAP or Mirah, but any file transfers between sites will be done via an approved secure platform such as secure send. Downloaded files will be stored on the psychology department's server, box.com, one drive, and/or google drive. The project coordinator will be regularly reviewing data for threats to data quality, such as missing data. Built-in validation protocols in REDCAP and Mirah will prevent entry of invalid responses.

Qualitative interview recordings, transcripts, and codes will also be stored securely on psychology department's server, box.com, one drive, and/or google drive.

13) Provisions to Monitor the Data to Ensure the Safety of Subjects*

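### Aim 2d mediation: the mechanism-to-outcome path should be split into within- and between-clinician parts, with only the within-clinician part used in the indirect effect

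*Combined protocol and SAP*

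**What the plan says.** In section 12 (Quantitative Analyses), the Aim 2c comparison is described as "We will examine differences in MBC outcomes by feedback condition, nesting within treating clinician and controlling for clinic". Clinic enters as a fixed effect: "In all Aim 2 models, we will treat site as a fixed effect". For Aim 2d, "we will extend the MLMs tested to accommodate potential mediators and moderation by NOT status, diagnosis, and treatment type", and then "Mediation will be tested using the products of coefficients method", with bootstrapped intervals. Before conditions are compared on mechanisms, session scores are aggregated into composites within therapist. The text does not make clear whether that yields one score per client, per therapist and condition, or per therapist.

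On allocation, section 10 (Procedures for effectiveness trial) says that as clients enter Mirah, "the system will automatically randomize them to either unidimensional or multidimensional MBC on a 1:1 ratio". No stratification by clinician is stated.

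The one relevant variance figure is in the sample size paragraph: "We assumed 8% of the outcome variance at the clinician level". That paragraph uses 22 clinicians for 900 youth and at least 22 for the 400-youth Research Subsample. Section 7 allows up to 200 clinicians.

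The documents do not mention centring a mediator, adding clinician means, fitting clinician fixed effects, or estimating separate b paths by level.

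**The concern.** The indirect effect is the product of a and b. Because each clinician treats clients in both arms, a mainly compares clients of the same clinician. In a random-intercept model with the mechanism score entered as it stands, b is a precision-weighted average of two slopes. One is the association among clients of the same clinician. The other is the association between clinician averages. The random intercept damps the second slope but does not remove it. The clinic fixed effect removes differences between clinics, not between clinicians in the same clinic.

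If some clinicians tend to obtain both better mechanism scores and lower symptom scores, the between-clinician slope is non-zero even when the mechanism does nothing for the individual client. The product then combines a within-clinician a with a partly between-clinician b, and the error runs in the hypothesised direction. Section 3 calls the pilot mechanism-driven, and section 4 says that it is meant to support a later R01. A falsely identified mediator could therefore steer the next trial.

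**Working it through.** The plan gives no figure for Aim 2d, so there is none to reproduce. The check asks how large b becomes when the true client-level b is zero.

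**Inputs from the documents.** Clinician share of outcome variance is ICC_Y = 0.08. N is 400, because the additional mechanism items are collected in the Research Subsample. The planning figure is 22 clinicians. Counts of 60 and 100 are used as possible values, given at least 22 in the subsample and up to 200 overall.

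**Assumed inputs.** The clinician share of mechanism variance (ICC_M) and the clinician-level correlation r are not in the documents. Three cases are used: mild (0.10, -0.3), mid (0.15, -0.5) and strong (0.25, -0.7). The sign is negative because a higher SFSS score is worse. The a path is taken as 0.25 to 0.40 SD.

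**Formulas**, with n clients per clinician:
- Between weight Wb = (n·ICC_M + 1 - ICC_M) / (1 - ICC_Y + n·ICC_Y)
- Within weight Ww = (n - 1)(1 - ICC_M) / (1 - ICC_Y)
- Share on the between slope w = Wb / (Wb + Ww)
- Between slope = r·√(ICC_M × ICC_Y) / (ICC_M + (1 - ICC_M)/n)
- Bias in b = w × between slope

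**Mid case, 22 clinicians.** n = 400/22 = 18.18.
- Wb = (2.727 + 0.85)/(0.92 + 1.454) = 1.507
- Ww = 17.18 × 0.85/0.92 = 15.87
- w = 1.507/17.38 = 0.087
- Between slope = -0.5 × √0.012 / (0.15 + 0.0468) = -0.0548/0.1968 = -0.278
- Bias = 0.087 × (-0.278) = -0.024

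With all variances near 1, the standard error of b is roughly 1/√400 = 0.05, so the bias is about 0.024/0.05 = 0.48 standard errors. The chance that b is declared significant is then Φ(-1.48) + Φ(-2.44) = 0.069 + 0.007, or about 7.7%. False mediation is slightly below this, because the a path must also be significant.

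The same steps for the other settings, beside false-mediation rates from simulation (random-intercept REML fits, true b = 0, both paths significant):

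| Clinicians | Case | w | Between slope | Bias in b | Approx. rate for b | Simulated false mediation |
|---|---|---|---|---|---|---|
| 22 | mild | 0.064 | -0.179 | -0.011 | 5.6% | 4.7-5.4% (a = 0.25-0.30) |
| 22 | mid | 0.087 | -0.278 | -0.024 | 7.7% | 5.3% (a = 0.25), 7.9% (a = 0.30), 7.5-9% (a = 0.40) |
| 22 | strong | 0.137 | -0.340 | -0.047 | 16% | 13-19% |
| 60 | mid | 0.196 | -0.197 | -0.039 | 12% | 9-13% |
| 100 | mid | 0.297 | -0.151 | -0.045 | 15% | 9-13% |
| 60 | strong | 0.265 | -0.273 | -0.072 | 30% | about 32% |
| 100 | strong | 0.366 | -0.226 | -0.083 | 38% | 34% to about 40% |

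In the mild case with 60-100 clinicians, simulation gives about 5% (4.8-5.7%) at a = 0.25-0.30. With 800 replicates, simulation error at 8% is 1.96 × √(0.08 × 0.92/800) = 1.9 points, so differences of one or two points between runs carry no meaning.

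The rate falls at a = 0.25 because the a path is itself often missed, not because the bias in b is smaller. Power for 0.25 SD with 200 per arm is about 0.705, so an unbiased b would give only 0.705 × 5% = 3.5%.

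**After the split** into clinician mean and deviation from it, simulated false mediation is about 3-6% in these cases and the mean within-clinician b is zero. If clinician effects on mechanism and outcome are uncorrelated, the unsplit model also stays at about 5%.

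**In effect terms.** With a = 0.4, the spurious indirect effect in the mid case is 0.4 × 0.025 = 0.010 SD at 22 clinicians and about 0.4 × 0.04 = 0.016 SD at 60-100.

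**The case against.** The strongest reply is that the plan is silent on centring and does not choose against it. It never says that the raw score will be entered, and an analyst could split the mediator without departing from the text. That stands: this is a gap in specification, not a stated error. The gap still matters, because without a rule the usual extension of the stated model is the unsplit one.

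Second, only the 8% comes from the documents. At 22 clinicians with mild correlation or a = 0.25, the false-mediation rate is at or near nominal, and the spurious effect is small. This also stands, and it limits the claim. It does not remove the direction of the bias or its growth as clients are spread over more clinicians.

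Third, the study is a pilot powered only for the Aim 2c outcome comparison. That lowers the stakes, but mediation is still a listed aim.

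A reader might infer three stronger things that the documents do not support:
- **That condition varies only within clinicians.** No stratification by clinician is stated, so the arm mix differs between clinicians by chance. The between-clinician share of the variance in condition is about 1/n, or 1/18.2 = 5.5% at 22 clinicians.
- **That the plan itself names clinician skill as a common cause of mechanism and outcome.** Section 4 (Background) says that "high-quality and continuous feedback will improve clinician competency, enhancing client outcomes". That is a claim about what feedback does, not about pre-existing skill. It makes a clinician-level correlation plausible, not established.
- **That most declared mediators would be false.** Rates above the ranges given here appear only with a near-perfect clinician correlation (0.9), a therapist-level composite, or clinician numbers near the ceiling of 200.

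**Conclusion.** The concern holds as a cheap improvement. As written, Aim 2d would multiply a mainly within-clinician a by a b that mixes two levels, and any positive link between clinicians' mechanism scores and their outcomes pushes the product towards mediation. The algebra is certain, but the size is not. It depends on the clinician share of mechanism variance, the clinician-level correlation and the a path, none of which the documents give. At the planning figure of 22 clinicians the effect ranges from negligible to moderate. It becomes substantial only with stronger correlation or with clients spread over many more clinicians. The documents do not support saying that the planned mediation results will be wrong, only that the plan leaves open an avoidable bias in a known direction.

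**What to change.** Make three changes to the Aim 2d text:
1. State that each mechanism composite is computed per client, not per therapist. With a therapist-level score, the deviation from the clinician's mean is zero for every client and the split cannot be run.
2. In the mediation models, enter the client's score minus the clinician's mean, together with the clinician's mean.
3. Form the indirect effect and its interval from the a path and the within-clinician b only. Report the between-clinician coefficient separately, as descriptive.

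The cost is a sentence or two of wording and one covariate, with no change to data collection. The standard error of b is about 4-8% larger at 22 clinicians and 10-25% larger at 60-100, so precision falls most where the bias is largest. The split removes clinician-level confounding only. Confounding of mechanism and outcome between clients of the same clinician remains and should be stated as a limitation.

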Aim 2c: Compare the effects of multidimensional and unidimensional MBC on proposed MBC mechanisms and youth outcomes.

Aim 2d: Examine whether the effects of MBC condition on outcomes are mediated by MBC mechanisms and/or moderated by OT/NOT status, diagnosis, and/or treatment type.

Aim 3: Conduct a mixed-methods analysis of implementation factors related to multidimensional or unidimensional MBC.

Aim 3a: Examine whether fidelity to MBC differs by condition.

Aim 3b: Examine whether implementation outcomes and challenges differ by MBC condition.

4) Background*

Approximately 14 to 20% of youth experience a mental disorder annually¹, with an estimated cost of \$247 billion dollars per year in the United States alone². Youth mental health concerns are often chronic and related to functional impairments including decreased educational attainment, juvenile justice involvement, and substance abuse^{1,3-7}. Data consistently point to a “quality chasm” between routine mental health services and evidence-based practices (EBPs)^{3,8}. Although numerous evidence-based treatments (EBTs) have been developed to address these concerns, results of effectiveness trials examining their performance in “as usual” clinical settings have yielded mixed results, and only small benefits over usual care on average⁹.

An approach to improving healthcare that holds great potential is Measurement Based Care (MBC). MBC is grounded in the frequent and systematic use of assessment to regularly track the processes and outcomes of care¹⁰ with feedback provided to clinicians^{11,12}. MBC has support as an EBP, with several meta-analyses¹³⁻¹⁸ and systematic reviews^{19,20} indicating a positive effect on patient outcomes, particularly in adult samples. As systematic quality measurement has been identified as a key component of organizational improvement by the Institute of Medicine⁸, MBC also supports data-informed decision-making for quality improvement²¹, paving the way for data-driven implementation of evidence-based practices. For ease of use and real-time data availability, MBC systems typically utilize technology for online measure administration and generation of feedback reports.

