In **Development Phase 2 (Aim 1b)**, we will develop algorithms to identify NOT and OT trajectories for the SFSS to generate alerts that will be embedded into the MBC feedback reports, support moderator analyses of intervention condition by OT/NOT effects, and set the stage for the randomization scheme for the R01 SMART. Analyses will utilize existing limited identifier datasets from 2 previous RCTs^{46,47}, including data from 597 youth treated by 165 clinicians using multidimensional MBC at 30 sites. During this phase, Mirah staff will also embed study measures into the system, update feedback reports with the alerts, and build a system to automate study randomization.

In **Development Phase 3 (Aim 1c)**, five clinicians will pilot the MBC system with up to 4 clients each; clinicians will select clients from their own caseloads based on the clinician's decision that it would be appropriate to begin using MBC with the client. Before beginning to treat their clients in the pre-pilot, clinicians will complete a packet of some or all of the baseline

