deterioration—a significant worsening of symptoms over the course of treatment—will be identified in the reference sample. Consistent with previous studies¹¹⁸⁻¹²⁰, identification of the base rate will be based on a combination of the reliable change index¹²⁷ (RCI) and clinical cutoff scores. Established SFSS values for the RCI and the clinical cutoff score¹²⁸ will be used to identify cases with clinical deterioration, operationalized as an SFSS increase over treatment exceeding the RCI and a case ending treatment in the clinically significant range of functioning. The deterioration base rate from the reference sample will serve as a basis for deriving prediction intervals around the expected mean change trajectory in the validation sample. Cases identified as exceeding the prediction interval at any point during treatment will comprise the NOT group. Cases within the interval form the OT group.

The validation sample will then be used to check the validity of the warning system in predicting true treatment deterioration. Analyses will examine whether classifying a client as NOT accurately predicts whether they end treatment classified as deteriorated. Sensitivity and specificity will be calculated and the algorithms will be adjusted as needed until adequate levels are reached, using Cannon et al.’s¹¹⁸ specificity values of .55 and specificity values of .75 as guides. We will then test the predictive validity of the finalized OT/NOT algorithm (**Aim 2a**) using the full RCT sample (N = 900). To prepare for the SMART R01, we will also conduct simulations, varying estimates entering the expected change trajectories to investigate transition points in the OT/NOT intervals to assess optimal timing of when to conduct the second randomization.

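### Aim 2d does not say when NOT status is assessed, and the only definition given is post-randomisation and built from the SFSS, so effects within NOT and OT clients can be biased by an amount the documents cannot fix

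*Combined protocol and SAP*

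**What the plan says.** Section 3 asks under Aim 2d whether condition effects are "mediated by MBC mechanisms and/or moderated by OT/NOT status, diagnosis, and/or treatment type". Section 12 (Quantitative Analyses) extends the outcome models: "Moderation by NOT status will be tested by entering NOT status, along with the feedback condition by NOT" status interaction and other covariates. It does not say when NOT is assessed, or whether it is fixed or time-varying.

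The one definition is in the Aim 1b text of Section 12: "Cases identified as exceeding the prediction interval at any point during treatment will comprise the NOT group". All other cases are OT. That sentence is written for the Aim 1b validation sample, but Section 10 (Development Phase 2) says the algorithm is meant to "support moderator analyses of intervention condition by OT/NOT effects".

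Three further statements matter:
- Allocation comes first. Section 10 states: "As the clinics add clients ages 11-17 to the Mirah system, the system will automatically randomize them".
- SFSS is a primary endpoint (Section 9) and the Aim 2c outcome: "MLM will also be used to compare the effects of study condition on SFSS change trajectories".
- NOT rates feed the next trial. Under Aim 2b they enter "power analyses that take into account rates of NOT/OT and projected attrition".

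**The concern.** If NOT means having crossed the interval at any session (ever-NOT), the moderator is a function of the outcome observed after allocation. Suppose multidimensional MBC lowers SFSS before some clients would have crossed. Those clients stay inside the interval and are counted as OT, while their counterparts in the unidimensional arm are counted as NOT. The NOT and OT groups then no longer contain the same kinds of client in each arm, and a comparison within either group is not a randomised one. Different completion does the same by another route, because fewer completed scores mean fewer chances to cross.

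The plan's own background makes both conditions plausible without establishing either. Section 4 describes alerts that prompt clinicians to change course, which would act after a crossing. It also describes feedback shared with clients that raises engagement, which needs no alert. It expects more burden, but possibly more acceptability, from the multidimensional battery. Aim 3a treats fidelity by condition as an open question, and Section 10 counts measure completion as part of fidelity.

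At stake are the reading of a named aim and the NOT/OT rates carried into the R01 design.

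**Working it through.** **Plan's own figure.** There is none to reproduce. The power text in Section 12 covers only the condition effect (Aim 2c). No figure is given for moderation, SFSS variances, interval width, NOT rate, effect path or completion by arm.

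**Case with no bias.** If condition acts only at or after first crossing and completion is equal, every score up to the first crossing is the same under either arm, so classification is the same. A simulation confirms it: NOT rate .41 in both arms; NOT effect -.353 against a true -.351; OT effect -.002 against 0.

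**Illustrative model (assumed).** Y(t) = a + b·t/12 + e, for intake (t = 0) and sessions 1 to 12.
- Intake SD is 1: Var(a) = r and Var(e) = 1 - r, with r = .5 or .7.
- SD of b is .3, .6 or .9.
- The upper limit is set around the overall mean or around an intake-specific trajectory.
- The limit is calibrated to 30% ever-NOT under unidimensional MBC.
- Each set has 200,000 clients. Higher SFSS is worse.
- Every client has the same true end-score effect, -.25 SD of the final SFSS (the d = .25 in the power text).

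Estimated effect in a group = mean final score of that group under multidimensional MBC minus the same under unidimensional MBC, with each arm classified on its own scores. Completion is equal.

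| Effect path | NOT | OT | NOT rate (uni v multi) |
|---|---|---|---|
| Linear from intake | -.18 to -.22 | -.18 to -.20 | 30% v 23-25% |
| Complete by session 3 | -.08 to -.13 | -.14 to -.17 | 30% v 18-22% |

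Range ends move by about .01 between runs. Share of the true effect lost = 1 - estimate/.25:
- Linear, NOT: 1 - .22/.25 = 12% to 1 - .18/.25 = 28%. OT: 20% to 28%.
- Early, NOT: 1 - .13/.25 = 48% to 1 - .08/.25 = 68%. OT: 32% to 44%.

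**Sign on trajectories.** With linear growth the true slope effect is -.25 per 12 sessions; estimates are -.24 to -.29 in NOT and -.19 to -.24 in OT. For the early path f(t) = min(t/3, 1), the true slope effect is -.25 × 12 × Σ(t-6)f(t)/Σ(t-6)² = -.25 × 12 × 10.67/182 = -.18. Over a wider grid of assumptions the NOT estimate runs from -.06 to -.22. So the NOT slope effect can be over- or understated.

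**Completion alone.** With no SFSS effect and assumed completion of 80% (unidimensional) v 60% (multidimensional), the spurious end-score effect is about .01 to .06 SD in NOT and .01 to .07 in OT. At 80% v 40% it reaches .13 and .16.

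**Interaction test.** With no true moderation and about 900 clients, it rejects in roughly 6-11% of runs at the nominal 5%, over the two sets of simulations made.

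**The case against.** The strongest reply is that this is an omission, not a demonstrated wrong analysis. The moderator sentence never says ever-NOT, and the definition was written for algorithm validation. Section 12 follows cited procedures that cannot be seen here, and Section 10 says procedures will be updated. That stands as a limit: the bias depends on an inferred definition and on how condition acts. It does not remove the problem. No other definition is given, Section 10 ties this algorithm to the moderator analysis, and no landmark, lag or caveat appears.

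Second, this is a pilot powered for Aim 2c only, the interaction test is close to its nominal level, and a landmark analysis costs power. All of that stands. It limits the severity and makes the landmark supplementary.

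Third, part of the reporting is already planned, since Aim 3a compares fidelity by condition. That covers measure completion but not NOT rates by arm.

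A reader might infer more than the documents support:
- That the bias is modest, or runs one way. The linear-growth figures suggest so, but the early path does not, and the plan gives no effect path.
- That the moderation test is invalid. The inflation found is mild; the within-group effects suffer more.
- That the main comparison is affected. Aim 2c does not condition on NOT status.
- That the same figures hold for the Ohio Scales. Only SFSS was examined.

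**Conclusion.** The point holds. Aim 2d leaves the timing of NOT status open, and the only available definition conditions on a post-randomisation variable built from a primary endpoint. If it is applied as written, effects within NOT and OT clients are biased whenever condition shifts SFSS before first crossing or shifts completion. They are unbiased if neither happens.

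The documents fix neither the size nor the sign. In the illustration, about an eighth to a quarter of a uniform benefit is lost in NOT clients with linear growth, and about half to two thirds with an early effect. Arm-dependent NOT rates would also carry into the R01 power work. These figures rest on assumed variances, 30% NOT, equal completion and SFSS as outcome. The point should be fixed, but it does not threaten the main comparison.

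**What to change.** In the Aim 2d text:

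1. State when NOT is assessed and whether it is fixed or time-varying.
2. Keep the ever-NOT interaction. Add a supplementary sensitivity analysis with NOT fixed at an early landmark (for example session 4), modelling only later SFSS. Set the landmark before trial data are analysed. The simulations already planned in Section 12, of "transition points in the OT/NOT intervals to assess optimal timing of when to conduct the second randomization", can inform it.
3. Report NOT rates and completed SFSS counts by arm.
4. State that ever-NOT subgroup effects condition on a post-randomisation, outcome-based variable and are not interpreted as causal subgroup effects.

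The cost is SAP wording and modest programming, with no new data. The landmark's price is power. For an assumed benefit of .31 in NOT clients only, growing linearly from intake, interaction power is about .77-.98 for ever-NOT on trajectories (partly produced by the bias itself) and .45-.74 on end score. A session-4 landmark has .14-.36 on later trajectories, or .31-.70 on the session-12 level using all later scores adjusted for first SFSS. With 30% NOT by session 12, only 14-20% have crossed by session 4, so later crossers are classed as OT. The landmark reduces the bias but does not remove it, and helps least when the effect is very early. It therefore supplements the ever-NOT test and does not replace it.
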